N/A	
Output ID: t_ae_ds_persae_*
 
 
● Analysis Populations: Safety Output will be repeated for different population combinations - please see the LoPO for details of these combinations
   
● Column Variables: Disease Status (Locally Advanced, Metastatic)
   
● Column Totals: Totals of non-missing Disease Status
   
● Analysis Variables: Total number of Patients with an Ongoing AE at discontinuation, Reason for Discontinuation from Treatment, Patient Died after Discontinuation from Treatment, Patient was Lost to Follow-Up After Discontinuation from Treatment, Latest Protocol Version Consented to
   
● Statistics and Calculation Methods: Use proq freq for events or proc sql for patient counts.
   
● Numeric Precision and Formatting of Statistics: Use AET02 standard template in the mockup
   
● Optional Subsetting: Reason for Discontinuation i.e. Death, Lost To Follow-Up. Patient Died After Discontinuation from Treatment i.e. 0-3 months, 0-6 months, >6 months after discontinuation.
 

Summary of Disposition of Patients with an AE ongoing at the time of Discontinuation (Latest Protocol Version consented to: 1 or 2) (Safety Population)

	Locally Advanced (N=282)	Metastatic (N=16)	Total (N=298)
Total number of patients with an ongoing AE at discontinuation	110 (39.0%)	12 (75.0%)	122 (40.9%)
Reason for Discontinuation from Treatment			
n	5 ( 1.8%)	1 ( 6.3%)	6 ( 2.0%)
Death	4 ( 1.4%)	1 ( 6.3%)	5 ( 1.7%)
Lost To Follow-Up	1 ( 0.4%)	0	1 ( 0.3%)
Patient Died After Discontinuation from Treatment			
n	4 ( 1.4%)	0	4 ( 1.3%)
0-3 months after discontinuation	3 ( 1.1%)	0	3 ( 1.0%)
0-6 months after discontinuation	1 ( 0.4%)	0	1 ( 0.3%)
Patient was Lost to Follow-Up After Discontinuation from Treatment			
n	12 ( 4.3%)	5 (31.3%)	17 ( 5.7%)
0-3 months after discontinuation	12 ( 4.3%)	5 (31.3%)	17 ( 5.7%)
Date of Treatment Discontinuation < 3 Months Before 6th November 2013			
n	6 ( 2.1%)	0	6 ( 2.0%)
Patients	6 ( 2.1%)	0	6 ( 2.0%)
Protocol Version Consented (Latest)			
n	110 (39.0%)	12 (75.0%)	122 (40.9%)
Version 1	21 ( 7.4%)	3 (18.8%)	24 ( 8.1%)
Version 2	89 (31.6%)	9 (56.3%)	98 (32.9%)

Programming Notes:

- Only include the AEs which were ongoing at the time of treatment discontinuation.

Number of Patients Reporting AEs by age group:

STREAM Template	Description

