## Deaths:

### Summary of Deaths:

STREAM Template	Description
N/A	
Output ID: t_dd_*
 

● Analysis Populations: Safety
 
● Column Variables: Disease Status (Locally Advanced, Metastatic)
 
● Column Totals: Totals of non-missing Disease Status
 
● Analysis Variables: Number of Patients Died, Primary Reason for Death
 
● Statistics and Calculation Methods: Use proc freq for events or proc sql for patient counts.
 
● Numeric Precision and Formatting of Statistics: Use DST01 standard template in the mockup
 
● Optional Subsetting: Primary Reason for Death: Adverse Event, Disease Progression, Other.

Summary of Deaths, Population : Safety-Evaluable Patients  
Protocol: M025616  
Snapshot Date: 03 August 2015. Clinical Cut-Off Date: 16 March 2015.  
File: t\_dd\_SE.

Status	Locally Advanced (N=1119)	Metastatic (N=96)	Total (N=1215)
Number of Patients who Died	92 (8.2%)	18 (18.8%)	110 (9.1%)
Primary Reason for Death	92 (8.2%)	18 (18.8%)	110 (9.1%)
Adverse Event	65 (5.8%)	6 (6.3%)	71 (5.8%)
Disease Progression	15 (1.3%)	12 (12.5%)	27 (2.2%)
Other	12 (1.1%)	0	12 (1.0%)

Program: /opt/BIOSTAT/prod/cdpt3616/mo25616/t\_dd.sas  
Output: /opt/BIOSTAT/prod/cdpt3616/i25616f/reports/t\_dd\_SE.out  
10SEP2015 19:09

Page 1 of 1

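### The disposition table for patients with an AE ongoing at discontinuation has overlapping death bands filled with disjoint counts, and gives its rows as percentages of a wider group than it describes

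*SAP*

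**What the plan says.** The output is specified in the Adverse Events section of the SAP, under the heading for disposition of patients with an AE ongoing at treatment discontinuation. Its analysis variables begin with "Total number of Patients with an Ongoing AE at discontinuation", followed by reason for stopping, death after stopping, loss to follow-up after stopping, and latest protocol version. The programming note reads "Only include the AEs which were ongoing at the time of treatment discontinuation". The optional subsetting gives the death bands as "Patient Died After Discontinuation from Treatment i.e. 0-3 months, 0-6 months" and a third band of more than 6 months. No denominator rule is given. The output is to be repeated for other population combinations.

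The populated shell covers safety patients whose latest consent was to version 1 or 2: 282 locally advanced, 16 metastatic, 298 in total. Of these, 110, 12 and 122 had an ongoing event at discontinuation. One shell row, absent from the list of analysis variables, is "Date of Treatment Discontinuation < 3 Months Before 6th November 2013". The Summary of Deaths shell in the same SAP carries "Snapshot Date: 03 August 2015. Clinical Cut-Off Date: 16 March 2015".

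**The concern.** A band running from 0 to 6 months contains the band from 0 to 3 months, so its count cannot be the smaller of the two. The shell shows 3 and then 1. Six months is also the SAP's own threshold. The listing of ongoing AEs for patients who discontinued (version 1 or 2, repeated for version 3 or higher) drops patients who died or were lost within six months, and the Potentially Reversible AE population applies the same limits. A reader who wants the number of deaths within six months would take the wrong row.

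The percentages raise a second, separate problem. The title, the programming note and the protocol-version block (n = 110, 12, 122) all say that the rows describe patients with an ongoing event. The percentages use the wider column N, so each is smaller than the rate among the patients described. Because the output is repeated for other populations, both features carry over to tables whose counts are not in the documents.

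**Working it through.** **Inputs**, all from the t_ae_ds_persae_* shell, as locally advanced / metastatic / total:
- column N: 282 / 16 / 298
- ongoing AE at discontinuation: 110 / 12 / 122
- lost to follow-up after discontinuation: 12 / 5 / 17, all in the row "0-3 months after discontinuation"
- died after discontinuation: n = 4 / 0 / 4; row 0-3 months 3 / 0 / 3; row 0-6 months 1 / 0 / 1
- latest consent version 1: 21 / 3 / 24; version 2: 89 / 9 / 98

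**Step 1: reproduce the printed percentages (count / column N).** Loss to follow-up: 12/282 = 4.3%, 5/16 = 31.3%, 17/298 = 5.7%. Deaths, total column: 4/298 = 1.3%, 3/298 = 1.0%, 1/298 = 0.3%. All match the shell, so the divisions are right on the column N.

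**Step 2: whom the rows describe.** Versions 1 and 2 sum to 21 + 89 = 110, 3 + 9 = 12 and 24 + 98 = 122. These are the patients with an ongoing event, not the column N.

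**Step 3: percentages on the patients described (count / number with an ongoing AE).**

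| Loss to follow-up | Printed | Among patients with an ongoing AE | Ratio |
|---|---|---|---|
| Locally advanced | 4.3% | 12/110 = 10.9% | 282/110 = 2.56 |
| Metastatic | 31.3% | 5/12 = 41.7% | 16/12 = 1.33 |
| Total | 5.7% | 17/122 = 13.9% | 298/122 = 2.44 |

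Exact 95% intervals: 8.3% to 21.4% for 17/122, and 15.2% to 72.3% for 5/12. Within a column the same ratio applies to every row after the first.

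**Step 4: death bands.** 3 + 1 = 4, which equals n. The counts are therefore disjoint, and nobody falls beyond 6 months. The row labelled 0-6 months holds deaths after 3 and up to 6 months. With exclusive bands on 122: 0-3 months 3 (2.5%), >3-6 months 1 (0.8%). Cumulatively, the count to six months is 4 (4/122 = 3.3%).

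**Step 5: sensitivity of the denominator.** The shell also lists 5 patients whose reason for stopping was death and 1 whose reason was loss to follow-up. The SAP does not say how they relate to the later rows. If the 5 deaths are assumed not to be at risk of later loss, the rate is 17/117 = 14.5%; if all 6 are removed, 17/116 = 14.7%. The choice hardly matters beside 5.7%.

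**The case against.** The strongest reply is that nothing is miscalculated. Each percentage reproduces on the N in its column header, 122 stands in the first row, and any reader can form 17/122. Showing percentages on the population N is a legitimate display choice. For deaths, n = 4 is printed directly above the bands. All of this stands, and it limits the point to labelling and presentation. It does not remove it: the nested bands are in the specification text as well as in the example, and with no denominator rule the shell is the only guidance a programmer has.

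Three stronger readings are tempting, and the documents do not support them.

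- A reader might infer that the table shows how much evidence on AE reversibility is missing. These are version 1 and 2 patients, with one month of planned follow-up. The Potentially Reversible AE population requires consent to version 3 or higher for that stated reason. Later follow-up for the 122 is largely absent by design, so neither 5.7% nor 13.9% measures that gap.
- A reader might infer that attrition is hidden most in the metastatic cohort. Its rate is the highest, but 31.3% is already printed, its dilution is the smallest (1.33-fold), and 5/12 is very imprecise.
- A reader might set 0.3% against 3.3% and infer a tenfold understatement of deaths. That comparison mixes a wrong label with a change of denominator, and the correct total is on the page.

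The 6 November 2013 row appears only in the example. It may be left over from an earlier data cut, though that is inference, and the cut-off rule sits in a separate specification that is not available here.

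**Conclusion.** The point holds as a minor reporting error in one descriptive safety table and its repeats. As labelled, the 0-6 months row gives 1 death where 4 are recorded within six months; the label is wrong and no death is lost. Printed loss to follow-up is 5.7% in total against 13.9% among the patients the table describes (locally advanced 4.3% against 10.9%, metastatic 31.3% against 41.7%).

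This rests on two assumptions: that the rows after the first are confined to patients with an ongoing event, as the title, programming note and version block indicate, and that the shell shows how the final table will be built. The sizes belong to the version 1 or 2 shell only; those for the repeats cannot be worked out from the documents. With one month of planned follow-up, 4 is the number of deaths recorded, which need not be all that occurred by six months. No hypothesis is tested in this trial, and no efficacy estimate depends on this table.

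**What to change.** In the specification of t_ae_ds_persae_* and its shell:

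1. Use exclusive bands of 0-3, >3-6 and >6 months, for both death and loss to follow-up.
2. Keep the column N as denominator for the first row only, and base the later rows on the number with an ongoing AE at discontinuation. Alternatively print both percentages, as the SAP's table of CPK elevations by maximum CTC grade already does.
3. If the recency row is kept, add it to the analysis variables and define it relative to the clinical cut-off of the analysis instead of a fixed 2013 date.

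The cost is a few lines of text and code, with no new data. The downside for the sponsor is that the printed attrition percentages become less favourable.

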## Listing of Ongoing Adverse Events for Patients who Discontinued Treatment (Latest Protocol Version Consented to: 3 or Higher)

Output ID: I\_ae\_ds\_PV3PLUS\_AEPERS\*

Repeat I\_ae\_ds\_PV1N2\_AEPERS\_\* output for Patients who latest consented to Protocol version 3 or higher.

## Listing of Adverse Events for Patients with Primary Reason of Death for Treatment Discontinuation

AEL02	
Output ID: l_ae_ds_dth*
 

● Analysis Population: Safety-Evaluatable Patients

● Column Variables: Disease status (Locally Advanced, Metastatic), Center/Patient ID/Cause of Death-Other Reason, Date of First Study Drug Administration, Adverse Event MedDRA Preferred Term, Study Day of Onset, AE Duration in Days, Most Extreme Intensity, Caused by Study Drug, Treatment for SAE, Action taken with Study Drug

● Column Totals: NA

● Analysis Variables: None

● Numeric Precision and Formatting of Statistics: Use standard display in the mockup

--------------	---

### Programming Note:

Only include patients who discontinued from Treatment due to Death.

## Listing of All Adverse Events

AEL02	
Output ID: I_ae_SE
 

● Analysis Population: Safety-Evaluable Patients

● Column Variables: Disease status (Locally Advanced, Metastatic), Center/Patient ID - Age/Sex/Race, Date of First Study Drug Administration, Adverse Event MedDRA Preferred Term, Study Day of Onset, AE Duration in Days, Serious, Most Extreme Intensity, Caused by Study Drug, Outcome, , Treatment for SAE, Action taken with Study Drug

● Column Totals: NA

● Analysis Variables: None

● Numeric Precision and Formatting of Statistics: Use standard display in the mockup

--------------	---

## Listing of Cause of Death On Study

AEL04	
Output ID: I_ae_dth_SE
 

● Analysis Population: Safety-Evaluable Patients

● Column Variables: Disease status (Locally Advanced, Metastatic), Center/Patient ID, Age/Sex/Race, Date of First Study Drug Administration, Date of Last Study Drug Administration, Day of Death, Cause of Death, Autopsy Performed?

● Column Totals: NA

● Analysis Variables: None

● Numeric Precision and Formatting of Statistics: Use standard display in the mockup

--------------	---

## Listing of Adverse Event Glossary

AEL01_NOLLT	
Output ID: I_ae_gloss_SE
 

● Analysis Population: Safety-Evaluable Patients

● Column Variables: MedDRA System Organ Class, MedDRA Preferred Term and Investigator-Specified Adverse Event Term.

● Column Totals: NA

● Analysis Variables: None

● Numeric Precision and Formatting of Statistics: Use standard display in the mockup

--------------------	---

### Programming Note:

- A glossary of all Adverse Events will be provided.
- Data will be ordered by MedDRA System Organ Class, MedDRA Preferred Term and Investigator-Specified Adverse Event Term.

Listing of Ongoing Adverse Events Ongoing at Treatment Discontinuation and still Ongoing 12 Months after Treatment Discontinuation:

STREAM Template	Description
N/A	
Output ID: l_ae_ongo_pt*
 
 
● Analysis Populations: Safety-Evaluable Patients with Protocol 3+ Subset, Excluding Patients who Discontinued Treatment within 6 months Output will be repeated for different AE Groups: Muscle Spasms, Alopecia, Ageusia, Dysgeusia and Weight Decreased
   
● Column Variables: Subject ID, Age, Sex, Disease Status, Treatment Discontinuation Date, Study Discontinuation Date and Reason, MedDRA Preferred Term, AE Start Date, Relativity to Treatment Discontinuation, AE End Date, AE Toxicity Grade and AE Outcome.
 

Programming Note:

- Data will be ordered by Subject ID, AE Start Date and AE End Date within each AE Group.

Listing of Ongoing Adverse Events Ongoing at Treatment Discontinuation and still Ongoing at Last Assessment (12 Months Follow Up):

STREAM Template	Description
N/A	
Output ID: I_ae_ongo_pt2*
 
 
● Analysis Populations: Safety-Evaluable Patients with Protocol Version 3 or more and who completed the 12 Months Follow Up Visit Output will be repeated for different AE Groups: Muscle Spasms, Alopecia, Ageusia, Dysgeusia and Weight Decreased
 
● Column Variables: Subject ID, Age, Sex, Disease Status, Treatment Discontinuation Date, Study Discontinuation Date and Reason, MedDRA Preferred Term, AE Start Date, Relativity to Treatment Discontinuation, AE End Date, AE Toxicity Grade and AE Outcome.
 

Programming Note:

- Complete for Patients who completed the study and their 12 month Follow Up Assessment
- Data will be ordered by Subject ID, AE Start Date and AE End Date within each AE Group.

Listing of Ongoing Adverse Events Ongoing at Treatment Discontinuation and still Ongoing at Last Assessment (12 Months Follow Up), Excluding Patients with Commercial Vismodegib:

STREAM Template	Description
N/A	
Output ID: I_ae_ongo_pt3*
 
 
● Analysis Populations: Safety-Evaluable Patients with Protocol Version 3 or more and who completed the 12 Months Follow Up Visit, but exclude any Patients who took commercial Vismodegib Output will be repeated for different AE Groups: Muscle Spasms, Alopecia, Ageusia, Dysgeusia and Weight Decreased
   
● Column Variables: Subject ID, Age, Sex, Disease Status, Treatment Discontinuation Date, Study Discontinuation Date and Reason, MedDRA Preferred Term, AE Start Date, Relativity to Treatment Discontinuation, AE End Date, AE Toxicity Grade and AE Outcome.
 

Programming Note:

- Exclude Patients who took commercial Vismodegib between treatment discontinuation and 12 months after treatment discontinuation.
- Data will be ordered by Subject ID, AE Start Date and AE End Date within each AE Group.

## Deaths:

### Summary of Deaths:

STREAM Template	Description
N/A	
Output ID: t_dd_*
 

● Analysis Populations: Safety
 
● Column Variables: Disease Status (Locally Advanced, Metastatic)
 
● Column Totals: Totals of non-missing Disease Status
 
● Analysis Variables: Number of Patients Died, Primary Reason for Death
 
● Statistics and Calculation Methods: Use proc freq for events or proc sql for patient counts.
 
● Numeric Precision and Formatting of Statistics: Use DST01 standard template in the mockup
 
● Optional Subsetting: Primary Reason for Death: Adverse Event, Disease Progression, Other.

Summary of Deaths, Population : Safety-Evaluable Patients  
Protocol: M025616  
Snapshot Date: 03 August 2015. Clinical Cut-Off Date: 16 March 2015.  
File: t\_dd\_SE.

Status	Locally Advanced (N=1119)	Metastatic (N=96)	Total (N=1215)
Number of Patients who Died	92 (8.2%)	18 (18.8%)	110 (9.1%)
Primary Reason for Death	92 (8.2%)	18 (18.8%)	110 (9.1%)
Adverse Event	65 (5.8%)	6 (6.3%)	71 (5.8%)
Disease Progression	15 (1.3%)	12 (12.5%)	27 (2.2%)
Other	12 (1.1%)	0	12 (1.0%)

Program: /opt/BIOSTAT/prod/cdpt3616/mo25616/t\_dd.sas  
Output: /opt/BIOSTAT/prod/cdpt3616/i25616f/reports/t\_dd\_SE.out  
10SEP2015 19:09

Page 1 of 1

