8.1.1 Primary Variables

The primary objective of this trial is to assess the safety of vismodegib in patients with locally advanced or metastatic BCC.

Consequently, the following safety variables are primary variables: all AEs, AEs Grade 3 or 4, AEs leading to drug interruptions or discontinuations, SAEs, cause of death on study, premature discontinuation from study and treatment, laboratory parameters (hematology and serum chemistry), and exposure to study medication.

Continuous data will be summarized using mean, standard deviation, median, minimum, and maximum. Discrete data will be summarized using frequencies and percentages. No adjustments for multiplicity of endpoints or within-subgroup comparisons will be used in the analyses.

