## Other Populations

### Potentially Reversible AE Population (PV3DSC6M)

The "Potentially Reversible AE" population is defined as the patients who consented to protocol version 3 or higher at any point during the study (from the CRF), excluding:

- Patients who discontinued treatment within 6 months of the cut (discontinue date from the CRF).
- Patients who were lost to follow-up within 6 months of treatment discontinuation (both from CRF).
- Patients who died within 6 months of treatment discontinuation (both from CRF).

The reason for inclusion of only patients who consented to version 3 or higher is due to the fact that patients consenting to earlier versions were only subject to a 1 month follow up period.

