## Disposition:

Patients will be considered to have completed the study if they have discontinued or completed treatment, and have completed their follow-up period (1 month for subjects who enrolled to protocol version 1 or 2, or 12 months for subjects who were enrolled to protocol 3 or later).

The reason for discontinuation of the study comes from the End of Follow Up CRF Page and should be listed under reasons for Study Discontinuation based on Safety and Non-safety categories.

Patients discontinued from treatment for a variety of reasons (recorded in the End of Study Treatment CRF page), and these should be listed under reasons for treatment discontinuation based on Safety and Non-safety categories.

Note: under the treatment discontinuation category, those who recorded “withdrew from treatment” in the CRF were assumed to have also left the study (as the investigators were additionally asked for study withdrawal information). As a result, patients who discontinued treatment but remained in follow-up were counted in the “Other” category. A footnote to the discontinuation table should be added to explain this idiosyncrasy.

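### The deaths summary pools all recorded deaths by cause with no window relative to last dose, although planned follow-up after last dose is 1 month for some patients and 12 months for others

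*SAP*

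**What the plan says.** Protocol 8.1.1 lists "cause of death on study" among the primary safety variables, and Protocol 8.2.2 says cause of death will be summarised and listed.

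The SAP's Summary of Deaths specifies the analysis variables as "Number of Patients Died, Primary Reason for Death" and the method as "Use proc freq for events or proc sql for patient counts". The columns are disease status and the denominator is the Safety population. The only time limit in the populated shell is the data cut: "Clinical Cut-Off Date: 16 March 2015". No limit is counted from last dose, and there is no person-time and no split by protocol version.

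The SAP's Disposition section gives the planned follow-up after treatment as "1 month for subjects who enrolled to protocol version 1 or 2, or 12 months for subjects who were enrolled to protocol 3 or later". Elsewhere, the SAP allows for this difference. The Potentially Reversible AE Population is limited to version 3 or later because "patients consenting to earlier versions were only subject to a 1 month follow up period". The deaths table has no such control.

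Three other outputs bear on the point. Overall survival is estimated by Kaplan-Meier with censoring at the last date known alive, in histologically confirmed patients. The Listing of Cause of Death On Study gives the last-dose date, day of death and cause for each patient. The AE and SAE summary tables are restricted to events with onset no later than 30 days after last dose (General AE Reporting).

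**The concern.** A death proportion has a clear meaning only if the period over which deaths were looked for is stated and is similar for the patients pooled. Here one row mixes three things: deaths on drug or shortly after, late deaths in patients scheduled for a year of visits, and whatever late deaths came to notice in patients scheduled for one month.

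The cause mix is the most exposed part. Deaths soon after last dose and deaths months later need not have the same causes, so the split between adverse event, progression and other depends partly on how long each group was observed. The collection rules may add to this. Under the current protocol (7.2.2), related serious events are reportable without time limit and unrelated ones for up to 12 months after last dose, so capture of late deaths may itself depend on cause. No planned summary adjusts cause of death for length of observation.

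**Working it through.** **1. Reproduce the plan's figures (Summary of Deaths shell).**
- Locally advanced: 92/1119 = 8.2%. Metastatic: 18/96 = 18.8%. Total: 110/1215 = 9.1%.
- Reasons, total column: adverse event 71/1215 = 5.8%; disease progression 27/1215 = 2.2%; other 12/1215 = 1.0%. The reasons sum to 71 + 27 + 12 = 110.
- As shares of deaths: 71/110 = 64.5%, 27/110 = 24.5%, 12/110 = 10.9%.

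All the stated percentages reproduce, so the arithmetic is sound. The question is what the proportions describe.

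**2. How many patients had the short planned follow-up?** The only count is in the shell for disposition of patients with an AE ongoing at discontinuation, latest version 1 or 2: 298 safety patients, 282 locally advanced and 16 metastatic. Against the deaths-table denominators:
- Total: 298/1215 = 24.5%.
- Locally advanced: 282/1119 = 25.2%.
- Metastatic: 16/96 = 16.7%.

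These shares are approximate. The version 1-2 shell refers to 6 November 2013 and the deaths shell uses a cut-off of 16 March 2015. The version split in 2015 is not given.

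**3. Does capture of deaths stop at the planned visit?** No. The SAP's Deaths paragraph under General Considerations takes the date of death from seven eCRF pages, including a survival follow-up page. The version 1-2 shell shows 4 deaths after discontinuation: 3 in the 0-3 month row and 1 in the 0-6 month row. The rows add to n = 4, so the last death lies beyond 3 months. Capture is not shown to be systematic, though. That shell covers only the 122 patients with an ongoing AE, and all 17 of their losses to follow-up after discontinuation fall at 0-3 months.

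**4. Illustration of size (assumption, not estimate).** Suppose the 298 still applied in 2015 and a fraction q of them died between 1 and 12 months after last dose without being recorded. Missed deaths m = 298q. Corrected proportion = (110 + m)/1215. The adverse-event share lies between 71/(110 + m), if no missed death was an adverse event, and (71 + m)/(110 + m), if all were.

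| q | m | Proportion died | Adverse-event share of deaths |
|---|---|---|---|
| 1% | 3.0 | 9.3% | 62.8% to 65.5% |
| 2% | 6.0 | 9.5% | 61.2% to 66.4% |
| 5% | 14.9 | 10.3% | 56.8% to 68.8% |
| 10% | 29.8 | 11.5% | 50.8% to 72.1% |

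**5. The other direction.** If a fraction f of the 110 deaths occurred more than 30 days after last dose, the proportion up to 30 days would be 110(1 - f)/1215: 8.15% at f = 10%, 6.79% at 25% and 4.53% at 50%. The documents do not give f.

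**6. Contrast between columns.** At q = 5% the locally advanced figure becomes (92 + 14.1)/1119 = 9.5% and the metastatic figure (18 + 0.8)/96 = 19.6%. The rises are 1.26 and 0.83 points, so the difference between columns moves by about 0.4 points. That is small beside 8.2% against 18.8%.

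**The case against.** The strongest reply is that the table does what the protocol asks. The variable is cause of death on study, described rather than tested, and a count to the cut-off is a legitimate description. All-cause death is handled by Kaplan-Meier, TEAEs leading to death have their own table, disposition separates 1-month from 12-month completers, and the listing lets a reader place each death in time. Much of this stands. The count should stay, and the all-cause question is largely answered by overall survival, provided censoring is non-informative. It does not answer the by-cause question. Overall survival ignores cause, and a listing is not a summary of a primary variable.

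Two stronger readings are tempting and are not supported:

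- A reader might infer that deaths are counted only to 1 month or 12 months after last dose, so that version 1-2 patients contribute almost only deaths on drug. The Disposition text defines when a patient has completed the study, not when death recording ends, and the evidence in step 3 goes against a hard stop.
- A reader might infer a definite understatement of 12-month mortality, for instance by assuming monthly death rates on and off drug. The documents give no deaths by time since last dose for the Safety population, so any such figure would reflect the rates assumed.

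It is also fair to say that protocol version is only one source of unequal observation. Patients still on treatment or in follow-up at the cut-off have had less time too.

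**Conclusion.** The point holds in a limited form. The deaths summary states no window relative to last dose and pools patients whose planned follow-up differs by 11 months. Its percentages and cause mix are therefore crude proportions over unequal observation, not risks over a defined period. The consequence is greatest for cause of death, which is a primary variable and has no other summary that allows for length of observation.

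The size is unknown. The ranges in step 4 rest on two assumptions: that the version 1-2 count can be carried from 2013 to 2015, and that the unrecorded fraction lies between 1% and 10%. Within them the overall proportion moves little at low q, while the cause mix becomes uncertain more quickly. The difference between disease groups is hardly affected. This is a worthwhile, inexpensive improvement. It does not invalidate the reported counts.

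**What to change.** Keep the overall count, labelled as all recorded deaths to the clinical cut-off, and add, by primary reason and disease status:

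- **(a)** Deaths from first dose to 30 days after last dose, in all safety patients. Every protocol version's planned follow-up covers this period. Time on drug still varies, so person-time alongside would help.
- **(b)** Deaths after day 30 and up to 12 months after last dose, in off-treatment patients whose latest consented version is 3 or higher and who were alive at day 30. Present cumulative incidence by cause, or deaths with person-time, censored at the last date known alive or the cut-off. If consent to version 3 came after day 30, time at risk should start at that consent.
- **(c)** Separate counts of late deaths in version 1-2 patients, and of any version 3-or-later deaths beyond 12 months, so that all blocks sum to the total.

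Add a footnote that the TEAE window is defined by AE onset, not date of death, so fatal-TEAE counts need not match block (a). Reconcile the Disposition text, which assigns follow-up by the version at enrolment, with its Programming Note, which uses the latest version consented to.

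The cost is one longer table and a smaller denominator in block (b). No new data are needed. The last-dose date, day of death and cause are already in the cause-of-death listing, consented versions are on the CRF, and the date last known alive is already derived for overall survival.
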